### **II. Hypotheses and Specific Aims:**

The PICLS (Pregnancy Intervention with a Closed-Loop System) Study is a two-center, prospective, 'open-label', single-blind, investigator-initiated randomized controlled pilot

study evaluating hybrid closed-loop (HCL) insulin delivery among pregnant women with T1D compared with sensor-augmented pump therapy (SAPT) throughout gestation and the first 6 weeks of the post-partum period at the Barbara Davis Center for Diabetes and Ohio State University. The HCL system being used is the Medtronic 670G system, which has been FDA-approved in non-pregnant populations but has never been studied in pregnancy.

**Specific Aim (SA) 1:** Evaluate safety of HCL therapy (Medtronic 670G with Guardian sensor) compared to SAPT in women with T1D throughout the 2nd and 3rd trimesters of gestation and the early post-partum period.

**Hypothesis SA 1.1:** We hypothesize that time spent with glucose <54 mg/dL will be the same or reduced among women using the HCL system compared to those using SAPT.

**Hypothesis SA 1.2:** We hypothesize that the episodes of diabetic ketoacidosis and rates of adverse skin reactions will be similar between groups.

**Specific Aim 2:** Evaluate indices of glucose control and fear of hypoglycemia in pregnant women with T1D using HCL therapy compared to those using SAPT throughout the 2nd and 3rd trimesters of gestation and in the early post-partum period.

**Hypothesis SA 2.1:** We hypothesize that HCL therapy will increase time spent in the glucose target range (63-140 mg/dL), reduce time spent in mild and more severe hypoglycemia (<63 mg/dL and <54 mg/dL, respectively), and reduce time spent in hyperglycemia (>140 mg/dL) over time compared to SAPT.

**Hypothesis SA 2.2:** We hypothesize that HCL therapy will reduce fear of hypoglycemia as measured by the Hypoglycemia Fear Survey, starting in the 1st trimester of pregnancy compared to SAPT.

**Specific Aim 3:** Evaluate quality of life and device acceptability in pregnant women with T1D using HCL therapy compared to those using SAPT throughout the 2nd and 3rd trimesters of gestation and in the early post-partum period.

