#### F. Data Analysis Plan:

##### Statistical Analysis Plan:

Data will be blinded to the study statistician. For the **interim safety analysis**, after the first 5 participants in each group have completed the 1st trimester, we will analyze the interim data to compare episodes of SH between groups to ensure no increased risk of SH with HCL therapy. Episodes of SH will be used for the interim analysis as SH events can be life-threatening for pregnant women and their fetuses. If interim safety analyses demonstrate no increased harm in either group, then the statistician will remain blinded until the end of the study. If the interim safety analyses demonstrate increased harm in one group necessitating evaluation of whether the study should be stopped, then the statistician will be unblinded at that point.

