To address **Specific Aim 1**, we will compare percent of time spent in the SH range of <54 mg/dL on CGM (primary outcome) using a non-inferiority t-test with a margin of 1%. Counts of DKA and adverse skin reactions (secondary outcomes) will be compared between groups (HCL vs. SAPT) using t-tests for normally distributed variables and Wilcoxon Rank-Sum test for non-normal variables. As the purpose of this study is to demonstrate that HCL has a similar safety profile compared to SAPT during pregnancy, we will use a non-inferiority test. As a secondary analysis of events such as SH, DKA, and skin reactions, we will account for potential differential follow-up times due to miscarriage, drop-out, and withdrawal using Poisson regression with an offset for follow-up time. To address **Specific Aim 2**, we will compare CGM glucose variables (primary outcomes for glucose variables will be time spent <54, <63, 63-140, >140, >180 mg/dL; secondary outcomes will be glucose SD, J index, HBGI, LBG, MAGE, and CONGAn) and fear of hypoglycemia score between groups (HCL vs. SAPT) using t-tests for normally distributed variables and Wilcoxon Rank-Sum test for non-normally distributed variables. We will examine the buckets of time spent in each range (hypoglycemia, in range, and hyperglycemia) by day and night, as well as day-to-day variation. Mean glucose variables and hypoglycemia fear scores will be compared during each trimester of pregnancy and 4-6 weeks post-partum using mixed models. To address **Specific Aim 3**, we will compare SF-36 scores, insulin device satisfaction and glucose device satisfaction by group (HCL vs. SAPT) using t-tests if scores are normally distributed and Wilcoxon Rank-Sum test if scores are non-normal. We will analyze changes in INSPIRE Questionnaire scores over time in the HCL group. **Specific Aim 4** is an exploratory aim, and for this aim we will examine rates of fetal loss, preeclampsia, cesarean section, LGA, and neonatal hypoglycemia using Chi-square tests. We will account for potential differential follow-up times due to miscarriage, drop-out, and withdrawal using Poisson regression with an offset for follow-up time as a sensitivity analysis, in addition to the proposed chi-square tests in the exploratory analyses of fetal loss, preeclampsia, Caesarean section, LGA, and neonatal hypoglycemia. We will use mixed models to analyze changes in repeated measures, such as glycemia variables and hypoglycemia fear scores by trimester. We will evaluate the percent of time spent in closed loop by trimester as a feasibility outcome that is important to the next step of a larger clinical trial with efficacy outcomes.

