
For women who discontinue CGM therapy during the study, we will do an intention to treat analysis of above-stated outcomes. The alpha level will be 0.05 for all analyses, except the non-inferiority tests (alpha = 0.025). The use of mixed models and Poisson regression will allow for analysis of data for the portion of the study completed with CGM therapy.

**Power and Sample Size Calculations:** The primary outcome for **Specific Aim 1** is percent of time spent <54 mg/dL on CGM. With a sample size of 10 women per group (20 study completers), we will have 80% power to detect non-inferiority using a one-sided alpha of 0.025 and a non-inferiority margin of 1.5% of time spent <54 mg/dL for HCL compared to SAPT, using estimates of variability from the PI's current study of CGM use during pregnancy. The standard deviation of time spent <54 mg/dL based on data from the PI's current study of CGM use during pregnancy was 1.1%. For **Specific Aim 2**, with a sample size of 10 women per group (20 study completers), we will have 83% power to detect a difference in time spent in target glucose range (65-140 mg/dL, this range was used in the power calculations because at that time there was no consensus on optimal time in range in pregnancy) of 3.3 hours/day (13.8%) between HCL to SAPT, assuming a standard deviation of 2.5 hours/day (effect size=1.0 SD). This is similar to effect sizes reported in another artificial pancreas study showing a difference of 2.5 hours/day (10.4%) between groups and a study of HCL in pregnancy (in a crossover design) showing a difference of 3.6 hours/day (15.2%). While this study is not powered to detect significant differences in maternal-fetal outcomes as described in **Specific Aim 4**, our goal is to provide estimates and preliminary data on these outcomes to inform the sample size needed for a larger trial focused on these outcomes, once the safety of the HCL system in pregnancy has been established.

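### The Aim 1 non-inferiority test carries two margins, 1% and 1.5%; the stated 80% power holds only for 1.5%, and falls to about 49% at 1% if the arms are truly equal

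*Combined protocol and SAP*

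**What the plan says.** Section IV.F (Data Analysis Plan) deals with the Aim 1 primary test twice.

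- **Statistical Analysis Plan, Specific Aim 1.** The outcome is set by "we will compare percent of time spent in the SH range of <54 mg/dL on CGM (primary outcome"), and it is to be tested "using a non-inferiority t-test with a margin of 1"%.
- **Power and Sample Size Calculations.** The Aim 1 primary outcome "is percent of time spent <54 mg/dL on CGM", which is the same variable. With 10 completers per group the text says "we will have 80% power to detect non-inferiority using a one-sided alpha of 0.025". The threshold attached to that power figure is "a non-inferiority margin of 1.5% of time spent <54 mg/dL for HCL compared to SAPT". The SD, taken from the investigator's earlier CGM study in pregnancy, is 1.1%.

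Alpha agrees in both places: 0.025 for non-inferiority tests. The power statement names no true difference. Hypothesis SA 1.1 in section II expects that "time spent with glucose <54 mg/dL will be the same or reduced among women using the HCL system", which admits equality.

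**The concern.** A non-inferiority margin is the decision threshold of the test, and a power figure belongs to one margin only. Here the margin in the analysis text is two-thirds of the margin on which the power was computed. Either the analyst has been given the wrong threshold, or the stated power does not describe the test that will be run.

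The plan says that its purpose is to show a similar safety profile for HCL, and section IV.G says the study would show whether the system is safe in pregnancy. With two margins on file, the one that yields the claim could be chosen after the data are seen.

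**Working it through.** **Inputs, all from section IV.F except the last**

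- SD of time below 54 mg/dL: 1.1 percentage points, taken as equal in both arms
- Completers: n = 10 per arm
- Alpha: 0.025 one-sided
- Margins: 1.0 (analysis text) and 1.5 (power text), both read as percentage points of time
- True difference HCL minus SAPT (d): not stated; 0 is assumed first and then varied

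**Formula.** Two-sample t-test with normal data. SE = SD × √(2/n) = 1.1 × √(2/10) = 0.4919. Degrees of freedom = 18, and the critical value is t(0.975) = 2.1009. Power = P(noncentral t > 2.1009), with noncentrality (margin − d)/SE.

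**Step 1: the plan's own figure.** Margin 1.5, d = 0: noncentrality 1.5/0.4919 = 3.049, power **82.2%**. Nine per arm gives 77.5%, so 10 is the smallest n that reaches 80%. An SD of 1.13, which rounds to 1.1, gives 80.1%. The stated 80% is therefore consistent with a 1.5-point margin and no true difference.

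**Step 2: the margin in the analysis text.** Margin 1.0, d = 0: noncentrality 1.0/0.4919 = 2.033, power **48.6%**. Reaching 80% takes 21 per arm (82.0%); 20 per arm falls just short.

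**Step 3: how far 48.6% depends on what was assumed.** All rows are for margin 1.0; the first row is the base case.

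| Input varied | Value | Power |
|---|---|---|
| Base case | d = 0, SD 1.1, 10 per arm | 48.6% |
| True difference | HCL 0.50 lower | 82.2% |
| | HCL 0.25 lower | 67.1% |
| | HCL 0.25 higher | 30.3% |
| SD | 0.75 | 80.5% |
| | 0.9 | 65.2% |
| | 1.3 | 37.0% |
| Women per arm | 12 (24 randomized, section IV.B) | 56.7% |
| | 14 (28 after run-in, section IV.C) | 63.9% |

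To restore 80% at margin 1.0 with 10 per arm, HCL must truly be about 0.46 point lower, or the SD must be about 0.75.

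**Step 4: effect on the decision.** Non-inferiority is shown when the observed difference plus 2.1009 × SE is below the margin. With an observed SD of 1.1 the half-width is 2.1009 × 0.4919 = 1.03 points. The largest passing difference is:

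- margin 1.5: 1.5 − 1.0335 = **+0.47**
- margin 1.0: 1.0 − 1.0335 = **−0.03**

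Between these limits the two statements give opposite answers on the same data. At the 1-point margin HCL must come out slightly better than SAPT to pass. Under equality the two disagree with probability 82.2% − 48.6% = 33.6%.

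**Step 5: what the wider margin allows.** If HCL truly adds a full point of time below 54 mg/dL, the test passes 2.5% of the time at margin 1.0 and 15.9% at margin 1.5.

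**The case against.** The strongest reply is that no calculation in the plan is wrong. The power text claims 80% only at 1.5 points, and that claim reproduces. On this view the 49% is a scenario that needs the 1-point margin to govern, true equality, an SD of 1.1 in both arms and normal data. Hypothesis SA 2.1 expects HCL to reduce time below 54 mg/dL, so equality is the cautious end of what the investigators expect. The SD comes from an earlier CGM study rather than from users of this device, and a percentage bounded at zero is unlikely to be normal with 10 per arm. The trial is also a pilot.

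Most of this is fair, and it limits how precisely the 49% should be read. It is one point in a range running from about 30% to 82% over the true differences and SDs shown above. None of it removes the contradiction. The power statement assumes no benefit of HCL, and using 24 or 28 women still leaves the 1-point test below 80% under equality.

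Reading one margin as relative and the other as absolute does not help: the 1.5 is tied to percent of time, its power reproduces only on that scale, and the analysis text names no other. Nor does the plan present 1.5 as a planning value. The same paragraph explains why its time-in-range limits differ from those analysed, but gives no such explanation for the margin. Pilot status does not make the point minor, because the plan intends to draw a safety conclusion from this test.

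**Conclusion.** The concern holds. Two current statements in section IV.F give different margins for the same primary safety test, and the plan does not say which governs. The stated 80% power is sound at 1.5 points (82.2% by exact calculation). At 1 point it is about 49% under equality and reaches 80% only if HCL is truly about 0.46 point lower or the SD is about 0.75. The conflict can decide the conclusion, since the two statements disagree in roughly one trial in three under equality. The power figures assume normal data, a common SD and margins in percentage points of time. The contradiction itself rests on none of these assumptions.

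**What to change.** State one margin, in percentage points of time below 54 mg/dL, in both the Specific Aim 1 analysis text and the power paragraph. Give a reason for it and the true difference assumed for the power.

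- **If 1 point governs:** restate the power as about 49% under equality with 10 completers per arm, preferably with the range over true difference and SD. Report the HCL minus SAPT difference with its 95% confidence interval, whose half-width is about 1.03 points at SD 1.1.
- **If 1.5 points governs:** correct the analysis text and justify the wider margin. The stated 80% then stands.

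The choice should be made and dated before any comparative data on this outcome are seen. Unblinding of the statistician is the latest limit, but not a safe one to rely on. If the interim safety analyses show no added harm "then the statistician will remain blinded until the end of the study", but a harm signal would bring unblinding earlier.

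The cost is wording only, with no extra patients or visits. The sponsor accepts either a less favourable power statement or the need to defend the wider margin.

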be asked to calibrate per device instructions, log self-monitored glucose values (7 per day), insulin doses, carbohydrate intake, and exercise. Women who are compliant with device wearing and log sheets, who do not have an adverse reaction to device adhesives or wearing, who are willing to wear the study devices, and who are otherwise deemed appropriate candidates by the study PI will be invited to continue in the study (see Figure 1). The operational definition of compliance for the run-in phase is device wearing for  $\geq 80\%$  of time during the run-in phase, changing infusion sets every 3-4 days, performance of a minimum of 2 finger-sticks per day (as the HCL system requires 2-4 calibrations per day), filling out  $\geq 80\%$  of the log sheets, successful remote uploading of the CGM data, and communication with the study team during the run-in phase. Women will also be asked to record dietary (food and beverage) intake for three days during the run-in phase using log sheets. Food records will be reviewed to assess dietary compliance with the personalized pregnancy nutrition goals provided to participants and carbohydrate counting skills. Targeted enrollment after the run-in phase will be 28 women and by the end of the study will be 20 women (10 completers per group allowing for a drop-out rate of 36% due screen failures, miscarriages, dropping out, or subjects being lost to follow up).

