**Figure 1: Overall Study Design**

\*2 weeks for pump-experienced participants at baseline and 4 weeks for pump-naïve participants at baseline.

\*\*Visits 7 through 14 for pregnancy care and study follow-up.

Abbreviations: CGM, continuous glucose monitor; HCL, hybrid closed-loop insulin therapy; SAPT, sensor-augmented pump therapy

Women meeting the above criteria will be trained to start SAPT mode with the Medtronic Minimed 670G insulin pump and Guardian CGM and will continue SAPT mode throughout the remainder of the 1st trimester of pregnancy. Insulin adjustments will be made every 1-7 days for the first 2 weeks. Frequency of insulin adjustments will be guided by participant experience with pump therapy, glucose levels, level of insulin sensitivity, and willingness to contact study staff to ask for assistance, where (in general) women with less pump experience, a larger-than-expected number of glucose levels above or below ADA targets, dramatic insulin sensitivity, and unwilling to proactively contact study staff for assistance will be contacted more frequently for pump follow-up and adjustments as necessary. Women will be counseled on the maternal and fetal health risks in pregnancies associated with T1D, on the ability to reduce these risks with optimal glycemic control, on

the ADA-recommended targets for glycemic control (HbA1c <6.5% prior to conception/1st trimester, HbA1c <6% as pregnancy progresses, fasting glucose target <95 mg/dL, 1-hour postprandial glucose target <140 mg/dL, and 2-hour postprandial glucose target <120 mg/dL if these can be achieved without significant hypoglycemia), and on the need for multidisciplinary care in pregnancy (diabetes expert, CDE, RD, RN, social worker, high-risk OB, eye provider, and other specialists as needed). Women with hypoglycemia unawareness will be given modified glycemic targets per ADA guidelines and the discretion of the clinical investigator. Women will be counseled on their individualized gestational weight gain goals based on guidelines from the Institute of Medicine and the American College of Gynecology, their body mass indices, lifestyle, and stage of pregnancy. They will be advised to contact the study team or study clinicians as needed to trouble shoot (e.g., for further pump adjustments, for re-training about using the 670G system, etc.) and to report AEs and SAEs throughout the duration of the study.

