At the beginning of the 2nd trimester, women will be randomized to HCL therapy or SAPT. Women who were on multiple daily injections at baseline will complete a minimum of 4 weeks of therapy in SAPT mode prior to being randomized. All women in the HCL arm will be trained on the HCL technology. For the first 2 weeks after training, women will be contacted daily for insulin adjustments (if applicable) and trouble-shooting of device wearing. Frequency of insulin adjustments will be guided by glucose levels, level of insulin resistance, and willingness to contact study staff to ask for assistance, where (in general) women with a larger-than-expected number of glucose levels above or below ADA targets, dramatic insulin resistance, and unwilling to proactively contact study staff for assistance will be contacted more frequently for pump follow-up and adjustments as necessary. For the HCL group, insulin adjustments will be changes to carbohydrate-to-insulin doses and/or active insulin time. For the SAPT group, insulin adjustments will be changes to basal rates, carbohydrate-to-insulin doses, correction factors, and/or active insulin time. The first 5 women in each arm of the study will be asked to complete 7-point profiles for 2 weeks after randomization. Women will attend research and clinic visits at the Barbara Davis Center and Ohio State University every 4 weeks for routine diabetes care in pregnancy, downloading of study devices, and outcomes measurements. CGM, glucose meter, and pump downloads will also be reviewed throughout the study to ensure compliance with treatment assignment and the study protocol. Insulin pump adjustments will be made at least once every 4 weeks at face-to-face clinic/research visits and every week in between face-to-face visits, as per routine clinical care. When recommendations for pump adjustments are made during the interim weekly remote monitoring, we will verify that participants correctly entered the new settings. Acceptable forms of verification will include, verbal or written confirmation of new pump settings by the participant, a new upload of settings in CareLink, sending screen shots or pictures of the new settings from the participant’s pump. Women will be contacted every week in between research visits to inquire about open- and closed-loop wear (HCL group) and for pump adjustments as needed (both groups) (See Table 2 and Figure 2). As per routine clinical care, we will recommend that women start low-dose aspirin therapy (81-162 mg orally daily) between 12 and 16 weeks gestations, to reduce the risk of preeclampsia, unless there is a contraindication to aspirin therapy. At the start of the 2nd and 3rd trimesters, women will be given handouts describing conditions of which they should be aware for that trimester (see appendix).

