Data Collection and Analyses: All glycemic data will be collected at each study visit. All other data will be collected at enrollment, 1st trimester (6-8 weeks gestation), 2nd trimester (18-20 weeks gestation), 3rd trimester (30-32 weeks gestation), and post-partum (4-6 weeks after delivery) except where otherwise indicated. Subjects enrolled between 8 weeks 1 day gestation and 11 weeks gestation who continue in the study after the run-in phase, will be allowed to complete the 1st trimester study assessments at the completion

of the run-in phase (outside the 6-8 week gestational time point). Each category of data and the pertinent specific aim (SA) to which it applies are outlined below.

(1) Screening (enrollment only): We will screen subjects with a history, physical exam, and urine or blood pregnancy test. Gestational age will be calculated based on the last menstrual period (or by viewing records of a uterine ultrasound). Subjects meeting inclusion/exclusion criteria will be invited to participate in the run-in phase. In our experience most women present to their diabetes provider for care during pregnancy prior to getting an ultrasound with an obstetrician. Eight to 11 weeks is the time frame when ultrasound dating is most accurate, but in our previous study 76.7% (33/43) of women presented prior to 8 weeks gestation. Thus, the LMP will be used for determining initial eligibility based on inclusion/exclusion criteria. Once an ultrasound is obtained, it will be used to determine the final gestational ages for each study visit.

(2) Run-in Phase: Subjects will wear the Medtronic Guardian CGM sensor continuously for 7 consecutive days. Subjects will calibrate per device instructions. Subjects will record self-monitoring blood glucose (SMBG) measurements (before meals, 2 hours after meals, and at bedtime), insulin doses, carbohydrate intake, and exercise on standardized log sheets. Subjects will be asked to download devices (glucose meter, insulin pump, and CGM) once during the run-in phase. The research staff will contact each subject after 2 days to ensure that they have access to communication methods in between research visits. Subjects will fill out a questionnaire about adverse reactions to device adhesives and wearing, as well as willingness to proceed further in the study.

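### The Aim 1 and Aim 2 between-arm tests use no baseline value, although pre-randomization CGM exists for every randomized woman, and the mixed models do not say how baseline enters

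*Combined protocol and SAP*

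**What the plan says.** Section F, Statistical Analysis Plan, gives three relevant instructions.

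- **Aim 1.** Time below 54 mg/dL is compared "using a non-inferiority t-test with a margin of 1" percentage point.
- **Aim 2.** CGM variables and fear of hypoglycemia are compared "between groups (HCL vs. SAPT) using t-tests for normally distributed variables and Wilcoxon Rank-Sum test for non-normally distributed variables".
- **Mixed models.** Mean glucose variables and fear scores "will be compared during each trimester of pregnancy and 4-6 weeks post-partum using mixed models". A later sentence adds: "We will use mixed models to analyze changes in repeated measures, such as glycemia variables and hypoglycemia fear scores by trimester".

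No sentence in Section F names a baseline covariate, ANCOVA or a group-by-time contrast.

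The baseline data are built into Section C and its data-collection list:

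- **Run-in.** "Subjects will wear the Medtronic Guardian CGM sensor continuously for 7 consecutive days". Compliance is a condition for continuing: "The operational definition of compliance for the run-in phase is device wearing for" at least 80% of the time, among other requirements.
- **SAPT lead-in.** Continuing women start the study pump and sensor in SAPT mode and "will continue SAPT mode throughout the remainder of the 1 st trimester of pregnancy".
- **Randomization.** "At the beginning of the 2 nd trimester, women will be randomized to HCL therapy or SAPT". Women who were on injections first complete at least 4 weeks of SAPT.
- **Fear survey.** Table 2 schedules questionnaires at visits 1 and 4-5, and randomization at visit 6.

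**The concern.** With 10 completers per arm, a baseline measure of the outcome is the cheapest source of extra precision. It also guards against arms that happen to start out different. The planned tests use none of it. The Aim 1 test carries the trial's safety conclusion, so the width of that confidence interval matters.

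The mixed models could recover the precision, but only if baseline enters suitably. The wording about changes permits a change-from-baseline contrast, which does worse than ignoring baseline when r is below 0.5. With the model unspecified, that choice could be made after the data are seen.

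**Working it through.** **Inputs from Section F, Power and Sample Size Calculations:** 10 per arm. Aim 1: SD 1.1 points, margin 1.5, one-sided alpha 0.025. Aim 2: difference 3.3 h/day, SD 2.5 h/day, alpha 0.05. The Aim 1 analysis paragraph gives a margin of 1. That conflict is a separate matter, so both margins are shown. **Assumed:** r, the correlation of the baseline with the outcome.

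**Step 1. The plan's own figures.** Standardized effects:

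- 1.5/1.1 = 1.36
- 1.0/1.1 = 0.91
- 3.3/2.5 = 1.32 (the text calls this 1.0 SD, but 83% power follows only from 1.32)

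For an unadjusted comparison, the noncentrality is effect/√(2/10) with 18 degrees of freedom.

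- Aim 1, margin 1.5: 1.364/0.447 = 3.05, power 82.2%. The plan states 80%, and 10 is the smallest group size that reaches it (9 per arm gives 77.5%).
- Aim 1, margin 1.0: 0.909/0.447 = 2.03, power 48.6%.
- Aim 2: 1.32/0.447 = 2.95, power 79.7% by the t distribution and 83.9% by the normal approximation. The plan states 83%.

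The stated figures are therefore those of an unadjusted two-sample comparison.

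**Step 2. ANCOVA.** Noncentrality = effect/√[(1−r²)(2/10)(1+F/18)] with 17 degrees of freedom, averaged over F(1,18) for chance baseline imbalance.

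**Step 3. Unadjusted change score.** The SD is multiplied by √(2(1−r)), with 18 degrees of freedom.

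| Analysis | Aim 1, margin 1.5 | Aim 1, margin 1.0 | Aim 2, 1.32 SD |
|---|---|---|---|
| Unadjusted | 82% | 49% | 80% |
| ANCOVA, r=0 | 80% | 46% | 77% |
| ANCOVA, r=0.3 | 83% | 50% | 81% |
| ANCOVA, r=0.5 | 90% | 58% | 88% |
| ANCOVA, r=0.7 | 97% | 74% | 96% |
| Change score, r=0.3 | 68% | 37% | 66% |
| Change score, r=0.5 | 82% | 49% | 80% |
| Change score, r=0.7 | 96% | 70% | 95% |

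ANCOVA breaks even with the unadjusted test at about r=0.25 in all three columns. A simulation of 100,000 trials per r agrees with the ANCOVA rows.

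**Step 4. Interval width.** The 95% half-width for time below 54 mg/dL is 2.101 × 1.1 × √0.2 = 1.03 points unadjusted. With ANCOVA, 2.110 × 1.1 × √[(1−r²) × 0.2 × (1+1/16)] gives 1.02 at r=0.3, 0.93 at r=0.5 and 0.76 at r=0.7.

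**Step 5. Chance imbalance.** The baseline difference between arms has SD √(2/10) = 0.447 baseline SDs. The probability that it exceeds 0.5 SD in either direction is 2(1−Φ(0.5/0.447)) = 26%, or about 13% in the direction against HCL.

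**Step 6. Skewness, Aim 1 only.** Simulated gamma-distributed outcomes (assumed mean 1.0, SD 1.1, margin 1.5; 20,000 trials) gave ANCOVA power of 81/83/88/95% at copula correlations 0/0.3/0.5/0.7, against about 83% unadjusted. The error rate at the margin was 2.1-2.2% with ANCOVA.

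**The case against.** The strongest reply is that nothing here is an error. The unadjusted tests hold their error rate under randomization, the trial is a pilot, and the gain rests on a correlation the documents do not give. The background section describes an insulin-sensitive first trimester, later resistance and a sharp post-partum fall, so early values may predict later ones weakly. Time below 54 mg/dL over a week or two is also a noisy baseline. At r=0.3 the gain is about 1 point. All of this stands, and it limits the point to a possible improvement.

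A second reply is that the planned comparison by trimester may already bring in first-trimester values. It may, so a reader should not infer that the plan ignores baseline altogether. But the role of those values is unstated, and these models are not the named Aim 1 non-inferiority test.

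Other stronger readings also lack support:

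- **Every woman has a baseline fear score.** The survey is scheduled, but completing it is not a condition for continuing.
- **Pump users have only 2 weeks of SAPT before randomization.** That figure is a footnote which Table 2 treats as a training period. The text continues SAPT for the rest of the first trimester.
- **Nothing limits baseline differences.** The A1C range of 5.5-9%, the exclusion for recent severe hypoglycemia and the compliance rule narrow the spread. The readable text names no stratification factor, but the design figures are not available.

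Finally, the Wilcoxon option protects against non-normality at 20 women. A fix that drops it without a rank-based replacement would lose something.

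**Conclusion.** The point holds as a cheap improvement, not as a flaw that invalidates the analysis. A reader might infer bias or an inflated false non-inferiority rate; averaged over randomizations there is neither. The loss is in precision and in protection against chance imbalance. At 10 per arm, adjustment changes power by −2 to −3 points at r=0, about +1 at r=0.3, +8 to +9 at r=0.5 and +15 to +26 at r=0.7. The unspecified mixed model is the more definite gap: read as an unadjusted change score, it would cost 12 to 14 points at r=0.3. These figures assume r, roughly normal outcomes, and the plan's own SDs and effects. The skewness check covers only Aim 1 at the 1.5-point margin.

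**What to change.** In Section F, Statistical Analysis Plan:

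1. Make the Aim 1 and Aim 2 comparisons of CGM outcomes and fear scores by ANCOVA, or by a mixed model with a stated group-by-time contrast, adjusted for the same measure before randomization.
2. Name the baseline. For CGM, use a fixed SAPT window ending at randomization, with the run-in week as fallback. For fear, use the last survey before randomization.
3. Take the non-inferiority confidence interval from that model.
4. State that a change score without baseline adjustment will not be used.
5. For clearly non-normal outcomes use a rank-based ANCOVA. Keep the unadjusted t-test or Wilcoxon test as a sensitivity analysis.

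Settle this before the statistician is unblinded. It needs new wording only, since the data are already scheduled for collection. The price is one degree of freedom, a loss of 2-3 points of power if r is 0, and no net gain below about r=0.25.
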